### 10.2 Prohibited Medications

Recombinant erythropoietin (rEPO) is not permitted at any time during the study. No other direct anti-leukemia therapy is permitted except for hydroxyurea in Cycle 1 to control or prevent signs/symptoms of leukostasis as required. Palliative radiation therapy may not be administered while the patient is on study except for management of localized leukemic infiltrates in the skin.

Patients must not receive medications that have a known risk to prolong the QT interval or induce Torsades de Pointes in light of the ability for gilteritinib to cause QT interval prolongation and the unknown potential for LANRA to do so (see [Appendix 4](#)).

*In vitro* data indicate that LANRA is predominantly metabolized by CYP3A4 in humans. As such, concurrent administration of strong CYP3A4 *inducers* is prohibited as these would be expected to cause reduced exposures to LANRA (see Section 6, LANRA Investigator Brochure; [Appendix 4](#)). Concurrent administration of strong CYP3A4 *inhibitors* should be avoided. If the use of a strong CYP3A4 inhibitor for patient management cannot be avoided, patients should interrupt treatment with LANRA for the time period that the strong CYP3A4 inhibitor is required\*. Administration of LANRA can resume at its previous dose 24 hours after discontinuation of the strong CYP3A4 inhibitor. Since grapefruit is known to be a strong inhibitor of CYP3A4, and Saint John's wort is known to be a strong inducer of CYP3A4, patients must be instructed to refrain from consumption of grapefruit, its juice, or Saint John's wort.

\*Most azole antifungal agents are strong CYP3A4 inhibitors (see [Appendix 4](#)), however, neither fluconazole nor isavuconazole are strong CYP3A inhibitors and can be concurrently administered with LANRA.

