#### **11.7.6 Adverse events**

During the Screening period, record only serious AEs. Beginning on C1D1 until the End-of-Treatment Evaluation, record all new AEs as well as any that predate C1D1 but that worsen in intensity or recur during the Treatment Phase. After the End-of-Treatment Evaluation, only serious AEs that are assessed as causally related to LANRA must be reported. Guidelines for the reporting of AEs and serious AEs are provided in [Section 16.0](#).

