## 16.6 Adverse Event Reporting Period

Report only SAEs after signing of the ICF, but before administration of study drug. Beginning on C1D1 until the End-of-Treatment Evaluation (or until initiation of new anticancer therapy, whichever is sooner), report all AEs regardless of the relationship to study treatment. Thereafter, only SAEs assessed as related to LANRA must be reported.

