- Grade 4 neutropenia or thrombocytopenia lasting > 28 days after treatment onset that is not attributed to active AML and at least possibly related to LANRA.

- Any toxicity resulting in reduction in the dose of LANRA in Cycle 1.

*In general, infection will not constitute a DLT unless it is assessed as having resulted from unexpectedly prolonged myelosuppression in the setting of < 5% blasts in the bone marrow, absence of myelodysplastic changes, and/or absence of AML by flow cytometry in the bone marrow.

Adverse Event

An AE is defined as any unfavorable or unintended sign, symptom, laboratory abnormality or disease (new or exacerbated) temporally associated with the use of a study drug, whether considered causally related to the study drug or not.

All AEs defined as reportable in Section 16.6 of the protocol will be recorded on the ADVERSE EVENTS CRF.

Treatment-emergent Adverse Event (TEAE)

Any adverse event that occurs on or after C1D1 and up to the End-of-Treatment visit following discontinuation of the last study drug is considered treatment-emergent.

Events that occur after the initiation of non-protocol anti-leukemic therapy will be considered as non-treatment emergent even if they occur before the End-of-Treatment visit.

Treatment-emergent Laboratory Toxicity (TELT)

A TELT is identified based on the laboratory data recorded in the eCRF and is defined as a National Cancer Institute - Common Toxicity Criteria for Adverse Events (NCI-CTCAE) v5.0 (NCI 2017) grade 1 or higher abnormality, which occurs on or after C1D1 and up to the End-of-Treatment visit and exhibits at least 1 grade shift from the baseline value.

Events that occur after the initiation of non-protocol anti-leukemic therapy will be considered as non-treatment emergent even if they occur before the End-of-Treatment visit.

Concomitant Medications

Concomitant medications are those medications taken on or after C1D1. This includes medications started prior to C1D1 and continued after C1D1. These medications will be recorded in the PRIOR/CONCOMITANT MEDICATION eCRF.

Prior Medications

Prior medications are those medications taken from the time of informed consent until C1D1. These medications will be recorded in the PRIOR/CONCOMITANT MEDICATION eCRF.

End of Study

After all enrolled patients either relapse or die or 5 years after the last patient enrolls (whichever is earlier) or if the sponsor decides to terminate the trial.

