10. PROPOSED TABLES, LISTINGS, AND FIGURES

Tables	
14.1.1	Subject Disposition and Discontinuation Summary, All Patients Enrolled: Phase 1b
14.1.2.1	Demographics, Safety Population : Phase 1b
14.1.2.2	Baseline Disease Characteristics, Safety Population : Phase 1b
14.1.4.1	Summary of Exposure, Safety Population: Phase 1b
14.1.4.2	Summary of Prior Antileukemic Regimens, Safety Population: Phase 1b
14.2.1	Summary of Best Response by ELN 2017 response criteria, Efficacy Evaluable Population: Phase 1b
14.2.2	Overall Survival, Safety Population: Phase 1b
14.3.1.1	Overview of Treatment Emergent Adverse Events, Safety Population: Phase 1b
14.3.1.2	Treatment-Emergent Adverse Events by System Organ Class, Preferred Term (All Cycles), Safety Population: Phase 1b
14.3.1.3	Treatment-Emergent Non-Serious Adverse Events by System Organ Class, Preferred Term (All Cycles), Safety Population: Phase 1b
14.3.1.4	Grade 3 or 4 Treatment-Emergent Adverse Events by System Organ Class, Preferred Term and Greatest Severity (All Cycles), Safety Population: Phase 1b
14.3.1.5	Treatment-Emergent Serious Adverse Events by System Organ Class, Preferred Term (All Cycles), Safety Population: Phase 1b
14.3.1.6	Treatment Related Adverse Events by System Organ Class, Preferred Term (All Cycles), Safety Population: Phase 1b

14.3.1.7	Treatment Emergent Adverse Events Leading to Dose Reduction by System Organ Class, Preferred Term (All Cycles), Safety Population: Phase 1b
14.3.1.8	Treatment Emergent Adverse Events Leading to Treatment Discontinuation by System Organ Class, Preferred Term (All Cycles), Safety Population: Phase 1b
14.3.1.9	Treatment Emergent Adverse Events Leading to Death by System Organ Class, Preferred Term (All Cycles), Safety Population: Phase 1b
14.3.2	Select Grade 3 or 4 Treatment-Emergent Laboratory Toxicities, All Cycles, Safety Population: Phase 1b
14.3.3	Electrocardiogram by Worst QTcF Results: Phase 1b
Listings	
16.2.1	Subject Disposition, All Patients Enrolled: Phase 1b
16.2.2.1	Informed Consent, All Patients Enrolled: Phase 1b
16.2.2.2	Subject Eligibility, All Patients Enrolled: Phase 1b
16.2.3	Analysis Populations, All Patients Enrolled: Phase 1b
16.2.4.1	Demographics, All Patients Enrolled: Phase 1b
16.2.4.2	General Medical History, All Patients Enrolled: Phase 1b
16.2.4.3	AML Diagnosis, All Patients Enrolled: Phase 1b
16.2.4.4	Additional AML Details, All Patients Enrolled: Phase 1b
16.2.4.5	Prior Systemic Anti-Leukemia Regimens, All Patients Enrolled: Phase 1b

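### LANRA-related SAEs that start after the treatment-emergent window are still collected but enter none of the planned SAE, related-AE or fatal-AE summaries, so those rates can only be undercounted

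*SAP*

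**What the plan says.** **Collection.** Protocol 16.6 sets the period for full reporting: from C1D1 "until the End-of-Treatment Evaluation (or until initiation of new anticancer therapy, whichever is sooner), report all AEs". It then continues: "Thereafter, only SAEs assessed as related to LANRA must be reported". Protocol 11.7.6 has the same late rule but ties it to the visit alone: "After the End-of-Treatment Evaluation, only serious AEs that are assessed as causally related to LANRA must be reported". The late events reach the AE data, because SAP 4.4.4 states: "All AEs defined as reportable in Section 16.6 of the protocol will be recorded on the ADVERSE EVENTS CRF".

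**Analysis.** SAP 4.4.4 counts an AE as treatment-emergent from C1D1 to the End-of-Treatment visit. It then adds that "Events that occur after the initiation of non-protocol anti-leukemic therapy will be considered as non-treatment emergent", even where that visit has not yet taken place. The laboratory-toxicity (TELT) definition has the same new-therapy cut-off. Footnote o to the assessment schedules, in both the protocol and the SAP, differs: an event qualifies if it starts or worsens between C1D1 and End-of-Treatment, and new therapy is not mentioned.

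**Reporting.** SAP 6.6.1 builds the AE summaries on TEAEs, including serious TEAEs and TEAEs related to LANRA. In SAP Section 10, Table 14.3.1.5 covers treatment-emergent SAEs and Table 14.3.1.9 is "Treatment Emergent Adverse Events Leading to Death by System Organ Class". Table 14.3.1.6 covers treatment-related AEs.

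**The concern.** The protocol deliberately keeps collecting one class of event after the window closes: serious events that the investigator attributes to LANRA. The SAP records them and then gives them no summary. Safety is the Phase 1b primary endpoint and is defined to include seriousness, causality and outcome. SAP Section 7 says that Phase 2 was not enrolled, so the Phase 1b tables are the trial's whole safety summary.

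The omission also sits oddly with the SAP's own caution elsewhere. SAP 4.4.4.2 counts an AE with missing causality as related, whereas here an event that has been positively judged related is left out of the rate.

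The window can also be short. End-of-Treatment falls 30 ± 7 days after the last dose, or earlier if new antileukemic therapy is to begin, and it must precede transplant (protocol 6.3). The SAP plans a listing of post-treatment transplants (16.2.5.6), so this path is foreseen.

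**Working it through.** The plan states no figure to reproduce. The check compares the windows, then goes through the outputs, then bounds the size.

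**1. The windows side by side**

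| Source | Full window closes at | After that |
|---|---|---|
| Protocol 16.6 (reporting) | End-of-Treatment or new anticancer therapy, whichever is first | LANRA-related SAEs |
| Protocol 11.7.6 (reporting) | End-of-Treatment | LANRA-related SAEs |
| Footnote o, protocol and SAP (TEAE) | End-of-Treatment; worsening counts | No provision |
| SAP 4.4.4 (TEAE) | End-of-Treatment or non-protocol anti-leukemic therapy; worsening not mentioned | Nothing qualifies; no exception |

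The End-of-Treatment visit falls 30 − 7 = 23 to 30 + 7 = 37 days after the last dose of either drug, or sooner if new therapy starts.

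**2. The planned AE tables (14.3.1.1 to 14.3.1.9)**

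- Eight of the nine are titled treatment-emergent, among them the SAE table (14.3.1.5) and the fatal-AE table (14.3.1.9).
- The ninth, 14.3.1.6, has no such limit in its title, but SAP 6.6.1 describes the summary as TEAEs related to LANRA.
- SAP 6.6.1 mentions events leading to death without a limit, but the title of 14.3.1.9 supplies one.
- None of the nine clearly includes a LANRA-related SAE with later onset, and no other table is planned for such events.

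**3. Where these events do appear**

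Listings 16.2.7.1 (AEs), 16.2.7.2 (SAEs) and 16.2.7.3 (deaths) cover all enrolled patients with no treatment-emergent limit. A late death also counts in the overall survival table (14.2.2), but without attribution to drug.

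**4. Which events are affected**

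The cut-off acts on onset: SAP 4.4.4.4 imputes start dates in order to decide treatment-emergence. An AE that starts inside the window and proves fatal later is still a TEAE. Only later-onset events drop out.

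**5. Size**

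SAP 6.6.1 counts patients: repeat events within a preferred term collapse to the most severe, and a patient counts once per system organ class. A late event therefore changes a rate only if the patient is not already counted in that row. The change is then 1/n, where n is the number of patients at the dose level. I assume n = 3 or 6 (the 3 + 3 cohort sizes) or 20 (the backfill cap):

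- n = 3: 1/3 = 33 percentage points
- n = 6: 1/6 = 17 percentage points
- n = 20: 1/20 = 5 percentage points

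In the column for all dose levels, with the maximum of 69 Phase 1b patients, it is 1/69 = 1.4 percentage points. A replaced patient who still belongs to the safety population would make n larger and the change smaller.

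**The case against.** The strongest reply is that the SAP window follows the protocol. Section 16.6 ends full AE reporting at the same two points, and footnote o ends treatment-emergence at End-of-Treatment. A duty to report late related SAEs does not make them treatment-emergent. Adding them to the TEAE counts would contradict footnote o and mix a period in which all AEs are collected with one in which only related SAEs are, over unequal follow-up. This stands, and it is why the remedy should not be a wider TEAE definition. It does not explain why the late events have no summary of their own.

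A second reply is that in a descriptive study of at most 69 Phase 1b patients a reader can find every such event in the listings. That is true, so a reader who infers that the events are lost or hidden goes too far. But a listing gives no rate by dose level, and the tables carry no sign that events lie outside them.

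Other stronger readings also fail:

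- **Every omitted event costs 1/n.** Patient-level counting makes this a maximum.
- **The undercount is probably large because patients often move quickly to new therapy.** The documents give no frequency for this and no count of late related SAEs.
- **Dose escalation is affected.** DLTs rest on the Cycle 1 criteria in protocol Appendix 1, not on the TEAE flag.
- **Patients given hydroxyurea while still on LANRA would routinely have later on-drug events reclassified.** Protocol 10.2 says "No other direct anti-leukemia therapy is permitted except for hydroxyurea in Cycle 1", and Section 13.0 makes use of a prohibited medication a reason for discontinuing study treatment, so the case generally needs a protocol deviation. Nor do the documents say that hydroxyurea for leukostasis is what the SAP means by non-protocol anti-leukemic therapy. What remains is a small drafting gap: the new-therapy cut-off does not require that study drug has stopped.

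**Conclusion.** The point holds for the summary tables. As planned, a LANRA-related SAE with onset after End-of-Treatment or after new therapy enters no related, serious or fatal AE rate. The direction is certain, since such omissions can only lower the rates. The size is bounded by 1/n per affected patient not already counted, and the number of such patients is unknown and may be zero.

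The conclusion rests on reading Table 14.3.1.6 through the text of SAP 6.6.1, and the death summary through the title of Table 14.3.1.9. If the sponsor intends either to cover all onsets, the SAP should say so. The listings and the overall survival analysis are complete in this respect.

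Separately, SAP 4.4.4 and footnote o define treatment-emergence differently, on worsening and on new therapy, and a programmer cannot follow both.

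**What to change.** 1. Keep the TEAE window. Beside Tables 14.3.1.5, 14.3.1.6 and 14.3.1.9, add a separate row or companion summary, by dose level, of all LANRA-related SAEs and LANRA-related fatal AEs regardless of onset.
2. Footnote how many of these fall after the cut-off, and state that counts after it rest on collection of LANRA-related SAEs only.
3. Reconcile the TEAE wording in SAP 4.4.4 with footnote o in both documents (worsening, and the new-therapy cut-off) and with the differing end-points in protocol 11.7.6 and 16.6.
4. State that the new-therapy cut-off in the TEAE and TELT definitions applies only after the last dose of both study drugs. Since 16.6 itself stops full AE reporting at new anticancer therapy without that condition, this brings in only AEs that sites did record.

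The cost is a short SAP revision, a flag in the AE dataset and a little programming. The late related SAEs are already collected, and no sample size or error rate changes. The related-SAE rate may look slightly less favourable.

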4.4.4.1. Presentations by Study Visits

All study visits should be scheduled relative to C1D1 regardless of any treatment interruptions. Visits will be presented according to the visit designation (eg, Cycle 1, Day 4) as recorded on the eCRF. If the same assessment(s) are collected multiple times within a given visit, the last non-missing value will be used for summary presentations. There are no windows for study visits from C1D1 through C1D16. Acceptable windows for study visits beginning on Cycle 1, Day 22 are ± 1 day. Unscheduled visits will not be included in by-visit data presentations but will be included in all tables of treatment-emergent laboratory toxicities. All data will be presented in data listings.

4.4.4.2. Missing Data

Every effort will be made to obtain required data at each scheduled evaluation from all enrolled patients. See [Section 4.4.4.4](#) for details of imputing missing dates. AEs with missing causal relationship will be assessed as related to study treatment. AEs with missing severity will be included in the denominator for all grade events of the same preferred term (PT) but will not be included in the numerator for any severity when reporting the frequency of events by severity.

Unless otherwise specified, all other missing data will not be imputed.

4.4.4.3. Imputation for Alphanumeric Data

Should there be instances where a clinical laboratory parameter is reported with imbedded non-numeric characters, as for example, “<0.1” or “>10”, the data will be imputed for quantitative summaries. The actual values as reported in the database will be presented in data listings.

For incorporation in quantitative summaries, the following imputation rules will be employed:

The limit of quantitation will be increased by one level of precision in the direction of the symbol that precedes the value. For example, “< 0.1” will be imputed to “0.09”, while “>0.1” will be imputed to “0.11”, and “>10” will be imputed to “10.1”.

4.4.4.4. Incomplete or Missing Dates

An incomplete date occurs when the exact date an event started or ended cannot be obtained. The database contains data fields for month, day, and year. A date is incomplete if at least one of these three fields is not known.

For many of the planned analyses, a complete date is necessary to determine if the event should be included in the analysis (eg, if an adverse event is treatment-emergent) or to establish the duration of an event. In such cases, incomplete or missing dates will be imputed.

For the purposes of handling partially reported start and stop dates for an event the following algorithm will be applied:

- Missing start day, but month and year present:
If the event occurs in the same month and year as C1D1, then the start day of the event will be assigned to the date corresponding to C1D1. For example, if an AE occurred in December 2021, and C1D1 was on 8 December 2021, the date of AE onset would be set to 8 December 2021.
Otherwise, the start day will be set to the first day of the month.
- Missing start day and month, but year present:
If event occurs in the same year as C1D1, then the start date of the event will be assigned to the C1D1 date. Following this rule, in the event a patient started treatment on 20 January 2022 and had an AE starting in 2022 with no Month and Day indicated, the AE date would be set to 20 January 2022.
Otherwise, the start day and month will be set to 01 January. Thus, for AEs with a start date of 2023 and initiation of LANRA in 2021, the AE start date would be 01 January 2023.
- Missing start day, month, and year will be set to C1D1.
- Missing end day, but month and year present:
The day will be set to the last day of the month.
- Missing end day and month, but year present:
The end day and month will be set to 31 December of that year or the study treatment completion date, if earlier.

If any imputed date causes the end date to occur prior to the start date of the event, the start date of the event will be used for the imputation of the end date. In data listings, start and stop dates of events will be displayed as reported on the eCRF (i.e., imputed values will not be listed).

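### SAP 4.4.4.4 sets incomplete adverse event start dates to C1D1 without checking the end date, so a screening event known to have ended before dosing can be counted as treatment-emergent

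*SAP*

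**What the plan says.** SAP 4.4.4.4 (Incomplete or Missing Dates) has three branches that send a start date to C1D1.

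- Day missing, month and year those of C1D1: "the start day of the event will be assigned to the date corresponding to C1D1".
- Day and month missing: "If event occurs in the same year as C1D1, then the start date of the event will be assigned to the C1D1 date".
- Nothing known: "Missing start day, month, and year will be set to C1D1".

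A start with a missing day in any other month is not moved to C1D1: "Otherwise, the start day will be set to the first day of the month".

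The section closes with a conflict rule. Its trigger is "If any imputed date causes the end date to occur prior to the start date of the event", and its remedy is that "the start date of the event will be used for the imputation of the end date". Listings show the dates as reported, not as imputed.

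SAP 6.6.1 applies these rules to missing onset dates of adverse events. SAP 4.4.4 defines a treatment-emergent event as "Any adverse event that occurs on or after C1D1 and up to the End-of-Treatment visit" after the last study drug is stopped. The Protocol's footnote to its assessment schedules (Tables 6 and 7) likewise requires onset or worsening from C1D1.

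Before dosing, Protocol 16.6 limits collection: "Report only SAEs after signing of the ICF, but before administration of study drug". Protocol 16.7.3 adds differentiation syndrome, which is collected from consent as an event of special interest. Screening lasts at most 21 days (Protocol 6.1).

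**The concern.** Setting an ambiguous onset to C1D1 is a sensible cautious convention. The difficulty arises when the timing is not ambiguous. If the recorded end is before C1D1, the start must be too, whatever part of it is missing. The SAP imputes these dates partly to decide whether an event is treatment-emergent. Here the recorded end already answers that question, and the rule returns the opposite answer.

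Adverse events are the primary endpoint of Phase 1b. A misclassified screening SAE would enter Table 14.3.1.2 (all treatment-emergent events) and Table 14.3.1.5 (serious ones), and Table 14.3.1.4 if Grade 3 or 4. If its causality were also missing, SAP 4.4.4.2 would count it as related. Because listings keep the reported dates, Listing 16.2.7.2 would show an event ending before C1D1 that the tables count as treatment-emergent. Stopping the trial after Phase 1b does not remove the issue, since these Phase 1b tables are still planned.

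**Working it through.** **Step 1: reproduce the SAP's own examples.** Applied literally, the rules give the three results printed in 4.4.4.4.

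- Start December 2021 with C1D1 on 8 December 2021 gives 8 December 2021.
- Start 2022 with C1D1 on 20 January 2022 gives 20 January 2022.
- Start 2023 with dosing begun in 2021 gives 1 January 2023.

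None of these examples has an end date.

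**Step 2: add an end date before dosing.** The C1D1 dates are the SAP's. The end dates, and the starts in cases C, D and E, are illustrative. An event is treated as treatment-emergent when its start, imputed where needed, is on or after C1D1.

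| Case | Reported start | Reported end | C1D1 | Start under SAP | Treatment-emergent under SAP? | Start and end with the fix |
|---|---|---|---|---|---|---|
| A | Dec 2021, day missing | 5 Dec 2021 | 8 Dec 2021 | 8 Dec 2021 | Yes | 1 Dec to 5 Dec; no |
| B | 2022 only | 10 Jan 2022 | 20 Jan 2022 | 20 Jan 2022 | Yes | 1 Jan to 10 Jan; no |
| C | Wholly missing | 3 Dec 2021 | 8 Dec 2021 | 8 Dec 2021 | Yes | 3 Dec to 3 Dec; no |
| D | Nov 2021, day missing | 3 Dec 2021 | 8 Dec 2021 | 1 Nov 2021 | No | Unchanged |
| E | 2021 only | Nov 2021, day missing | 8 Dec 2021 | 8 Dec 2021 | Yes | 1 Jan to 30 Nov; no |

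For the case A pattern, the possible recorded end days before C1D1 are 1 to 7 December. All 7 of 7 are classed as treatment-emergent under the SAP, and 0 of 7 with the fix.

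**Step 3: does the closing sentence matter?** In case A the end (5 December) precedes the imputed start (8 December).

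- If the sentence covers recorded end dates, the end becomes 8 December and the record reads as a one-day event on C1D1.
- If it covers only imputed end dates, the end stays at 5 December and the record ends three days before it starts.

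The start is 8 December either way, so the classification is the same.

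**Step 4: which events are exposed?** The earliest screening day for C1D1 on 8 December 2021 is 8 December minus 21 days, or 17 November. For C1D1 on 20 January 2022 it is 30 December 2021. Within that window only SAEs and differentiation syndrome are collected.

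**Step 5: size.** If the patient has no other treatment-emergent SAE, one misclassified event adds 1/n to the rate.

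- n=3: 1/3 = 33 points.
- n=6: 1/6 = 17 points.
- n=20 (the cap for a backfilled cohort): 1/20 = 5 points.
- n=69 (the Phase 1b maximum): 1/69 = 1.4 points overall.

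**The case against.** The strongest reply is that the trigger is very unlikely. It needs a screening SAE with an unknown start day and a known end before C1D1. SAEs are reported to the sponsor within 24 hours with follow-up reports (Protocol 16.7.4), and the database is cleaned before lock. The direction is also cautious, matching the SAP's choice to count missing causality as related. Both points stand. They make this a small matter, but they do not justify overriding a recorded date that settles the timing.

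A second reply is that the closing sentence was never meant to touch recorded dates. The section concerns incomplete or missing dates, and the sentence has an ordinary use: a year-only end date capped at treatment completion can fall before the start of a late event. That reading is reasonable, although the trigger's reference to any imputed date leaves it open. A reader might infer that the SAP definitely overwrites recorded end dates and that this causes the error. The first is only one reading, and Step 3 shows that the second is not so.

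Three further inferences are not supported.

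- Medications: the concomitant definition also turns on C1D1, but SAP 6.6.4 only lists medications, in one combined listing with reported dates. No planned medication table changes.
- Year-only starts: the branch spans 1 January to C1D1 on paper, but adverse events are exposed only within the screening window.
- Dose escalation: nothing shows that the Dose Escalation Committee's decisions depend on these imputed dates.

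**Conclusion.** The rule as written gives a wrong classification for a narrow set of records: SAEs or differentiation syndrome events in screening, with a start that falls in one of the three C1D1 branches and a recorded end (complete, or partial but clearly before C1D1) that precedes dosing. The error always inflates treatment-emergent counts. For one affected patient with no other treatment-emergent SAE, the cohort rate moves by 5 to 33 points for n from 20 down to 3. The larger figures belong to cohorts of 3 to 6 without backfill.

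This assumes that treatment emergence is programmed on the imputed onset, as SAP 6.6.1 indicates. The documents do not say how many such records exist. The expectation is few or none, so the point is minor, but the planned tables and listings would disagree for any that do.

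**What to change.** Amend SAP 4.4.4.4 as follows.

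1. Use C1D1 as the default start only when the end date is missing, ongoing, or on or after C1D1.
2. If the end date, complete or partial, shows that the event was over before C1D1, set the start to the earliest date consistent with its recorded parts, or to the end date if the start is wholly missing. Class the event as not treatment-emergent.
3. State that a fully recorded end date is never replaced, and confine the closing sentence to imputed end dates.

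The cost is a few sentences and a small programming change. The cautious default is kept wherever the timing is unknown. A count of records with an incomplete start and an end before C1D1 would show at once whether any table is affected.
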